1 SYNOPSIS

Title of Study:	A Phase 1 Study to Investigate the Absorption, Metabolism, and Excretion of [¹⁴ C]-BVD-523 Following Single Oral Dose Administration in Healthy Male Subjects
Objectives:	
The primary objective of this study is to characterize the metabolic disposition, pharmacokinetics (PK), and routes of elimination of [¹⁴C] labeled BVD-523 after administration of a single, oral dose to healthy male subjects.
 
The secondary objective of this study is to evaluate the safety and tolerability of a single oral dose of [¹⁴C] labeled BVD-523 in healthy male subjects.

Methodology/Study Design:	This is an open-label, absorption, metabolism, and excretion study. Blood/plasma, urine, and fecal samples for bioanalytical, radioanalytical, and metabolism analysis, as applicable, will be obtained through 168 hours postdose. If Discharge occurs after Day 8, additional samples (blood/plasma, urine, and fecal) for radioanalysis will be collected every 24 hours until Discharge.
Number of Subjects:	Six healthy male subjects will be enrolled and dosed on Day 1 to complete at least 4 subjects.
Diagnosis and Main Criteria for Inclusion:	Healthy male subjects between 18 and 65 years of age, inclusive, with a body mass index of 18.5 to 32.0 kg/m ² , inclusive.
Test Product(s), Dose, and Mode of Administration:	Subjects will receive a single oral 600-mg (4 × 150-mg capsules) dose of BVD-523 containing approximately 200 μCi of [¹⁴ C] labeled BVD-523 following a 2-hour fast that follows breakfast.
Duration of Treatment:	
Planned Enrollment/Screening Duration: up to 27 days (Days -28 to -2)
 
Length of Confinement: up to 16 days (Day -1 to Day 15)
 
Planned Study Conduct Duration (Screening to Discharge): up to 43 days

Criteria for Evaluation: Safety	Safety endpoints for this study include: incidence, nature, and severity of adverse events (AEs), clinically significant changes in results of clinical laboratory evaluations, vital signs measurements, 12-lead electrocardiograms (ECGs), and physical examination (PE) findings.

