Sample collection and confinement will continue until discharge criteria are met or the maximum stay is reached. Subjects experiencing emesis during the first 4 hours postdose may be discharged on the same day from the clinical site, provided there are no safety concerns, and after follow-up study procedures are performed.

In this study design, safety will be monitored with AE inquiries, clinical laboratory evaluations ([Appendix A](#)), vital signs measurements, 12-lead ECGs, and PE findings during the study.

Blood/plasma, urine, and fecal samples will be collected for bioanalytical, radioanalytical, and metabolism analysis through 168 hours postdose. If Discharge occurs after Day 8, additional samples (blood/plasma, urine, and fecal) for radioanalysis will be collected every 24 hours until Discharge. A study flow chart is presented in [Table 6-1](#).

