5.3 Removal of Subjects from Study Participation

Subjects will be informed that they are free to withdraw from the study at any time and for any reason. The Investigator (or designee) may remove a subject from the study if, in the Investigator's (or designee's) opinion, it is not in the best interest of the subject to continue the study. Subjects may be withdrawn due to the following: change in compliance with inclusion/exclusion criterion that is clinically relevant and affects subject safety, occurrence of AEs, intake of nonpermitted concomitant medication that might affect subject safety or study assessments/objectives, etc. Notification of withdrawal will immediately be made to the Sponsor's Study Monitor. In case of withdrawal of study participation, efforts will be made to perform all final study day assessments ([Table 6-1](#)). The date the subject is withdrawn from the study and the reason for withdrawal will be recorded on the subject's electronic Case Report Form (eCRF). All withdrawn subjects will be followed until resolution of all their AEs or until the unresolved AEs are judged by the Investigator (or designee) to have stabilized.

The entire study may be discontinued at the discretion of the Investigator (or designee), Sponsor, or Sponsor's Medical Monitor based on the occurrence of the following:

- AEs unknown to date with respect to their nature, severity, and/or duration;
- Increased frequency and/or severity and/or duration of known AEs;
- Medical or ethical reasons affecting the continued performance of the study;
- Difficulties in the recruitment of subjects;
- Cancellation of drug development.

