of total radioactivity in plasma
 AUC_{0-24} Plasma Metabolites/Total Radioactivity Ratio
 AUC_{0-24} of nonradiolabeled metabolites in plasma/ AUC_{0-24}
of total radioactivity in plasma

In addition, the following PK parameters will be calculated, whenever possible, for each subject based on the urine concentrations of BVD-523 and total radioactivity:

A_{eu} amount excreted in urine over sampling interval
Cumulative A_{eu} cumulative amount excreted in urine, calculated as the sum of the amount excreted in urine for each collection period
 CL_R renal clearance, where $CL_R = A_e/AUC_{0-\infty}$ (for BVD-523 only)
 $\% F_{eu}$ percent of dose excreted in urine over sampling interval, where $\% \text{ Excreted} = 100 (A_{eu}/\text{dose})$
Cumulative $\% F_{eu}$ cumulative percent of dose excreted in urine, calculated as the sum of the percent of dose excreted in urine for each collection period

The following PK parameters will be calculated, whenever possible, for each subject based on the fecal concentrations of total radioactivity:

A_{ef} amount excreted in the feces over sampling interval
Cumulative A_{ef} cumulative amount excreted in feces, calculated as the sum of the amount excreted in feces for each collection period
 $\% F_{ef}$ percent of dose excreted in feces over sampling interval, where $\% \text{ Excreted} = 100 (A_{ef}/\text{dose})$
Cumulative $\% F_{ef}$

cumulative percent of dose excreted in feces, calculated as the sum of the percent of dose excreted in feces for each collection period

Pharmacokinetic calculations will be performed, if appropriate, using commercial software such as Phoenix™ WinNonlin® (Certara USA, Inc., Version 6.4 or higher).

Pharmacokinetic parameters for the metabolites of [¹⁴C]-BVD-523 may be calculated, as deemed appropriate, based on plasma, urine, and fecal concentration levels.

Appropriate analyte ratios will be based on relevant AUC values. Other parameters may be added as appropriate. Final PK parameters reported will be detailed in the Statistical Analysis Plan (SAP).

Pharmacokinetic analysis will use actual times as recorded in the eCRF. Other data handling procedures will be detailed in the SAP.

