AUC _{0-∞} Plasma Metabolites/ Total Radioactivity Ratio	AUC _{0-∞} of nonradiolabeled metabolites in plasma/AUC _{0-∞} of total radioactivity in plasma
AUC ₀₋₁₂ Plasma Metabolites/ Total Radioactivity Ratio	AUC ₀₋₁₂ of nonradiolabeled metabolites in plasma/AUC ₀₋₁₂ of total radioactivity in plasma
AUC ₀₋₂₄ Plasma Metabolites/ Total Radioactivity Ratio	AUC ₀₋₂₄ of nonradiolabeled metabolites in plasma/AUC ₀₋₂₄ of total radioactivity in plasma

In addition, the following PK parameters will be calculated, whenever possible, for each subject based on the urine concentrations of BVD-523 and total radioactivity. Parameters for BVD-523 in urine will be calculated and reported by the Covance EC Biometrics PK group; parameters for total radioactivity (except CL_R, which will be calculated for BVD-523 only) will be calculated and reported by the Covance Radioanalysis group. Urinary parameters for total radioactivity will also be presented in the CSR tables.

Parameter	Definition
A_{eu}	amount excreted in urine over sampling interval (t1-t2) where t1 and t2 are the start and end times of the sampling interval, respectively
Cumulative A_{eu}	cumulative amount excreted in urine, calculated as the sum of the amount excreted in urine for each collection interval
CL_R	renal clearance, where $CL_R = A_{eu}/AUC_{0-\infty}$ (for BVD-523 only)
% F_{eu}	percent of dose excreted in urine over sampling interval (t1-t2), where % Excreted = $100 (A_{eu}/\text{dose})$
Cumulative % F_{eu}	cumulative percent of dose excreted in urine, calculated as the sum of the percent of dose excreted in urine for each collection interval

The following PK parameters will be calculated, whenever possible, for each subject based on the fecal concentrations of total radioactivity. Parameters for total radioactivity will be reported by the Covance Radioanalysis group in the Radioanalysis report. Fecal parameters for total radioactivity will also be presented in the CSR tables.

Parameter	Definition
A_{ef}	amount excreted in feces over sampling interval (t1-t2)
Cumulative A_{ef}	cumulative amount excreted in feces, calculated as the sum of the amount excreted in feces for each collection interval
% F_{ef}	percent of dose excreted in feces over sampling interval (t1-t2), where % Excreted = $100 (A_{ef}/\text{dose})$
Cumulative % F_{ef}	cumulative percent of dose excreted in feces, calculated as the sum of the percent of dose excreted in feces for each collection interval

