Additional PK parameters may be determined where appropriate.

Pharmacokinetic analysis will, where possible, be carried out using actual postdose times recorded in the raw data. If actual times are missing, nominal times may be used with sponsor approval.

Concentrations are used as supplied by the analytical laboratory for PK analysis. The units of concentration and resulting PK parameters, with amount or concentration in the unit, will be presented as they are received from the analytical laboratory.

C_{\max} and T_{\max} will be obtained directly from the plasma concentration-time profiles.

For multiple peaks, the highest postdose concentration will be reported as C_{\max} . In the case that multiple peaks are of equal magnitude, the earliest T_{\max} will be reported.

The amount excreted in urine (A_{eu}) for each urine collection interval will be calculated as the product of urine concentration and urine weight; Cumulative A_{eu} 0-x hour will be calculated by summing the A_{eu} values for each collection interval over the 0-x hour period.

In addition to the PK and radioanalysis results, a discussion of the results of metabolite characterization will be included in the CSR however no tables, figures, or listings will be generated. The quantitation of parent and metabolites (concentrations and/or percent of dose), as applicable, other applicable metabolite characterization results (representative chromatograms, proposed metabolite structures, etc.), and any PK parameters calculated from the radiochromatography data will be reported in the Metabolite Profiling and Identification report. Radiochromatography PK parameters may be summarized in the CSR along with PK parameters determined from the bioanalytical data.

10.3.1.1 Criteria For Handling Concentrations below the Limit of Quantification in Pharmacokinetic Analysis

Concentration values that are below the lower level of quantification (BLOQ) will be set to zero, with defined exceptions as follows;

- Any embedded BLOQ value (between 2 quantifiable concentrations) and BLOQ values following the last quantifiable concentration in a profile will be set to missing for the purposes of PK analysis.
- If there are late positive concentration values following 2 BLOQ concentration values in the apparent terminal phase, these values will be evaluated. If these values are considered to be anomalous, they will be set to missing.

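### Renal clearance is printed as a single-interval urine amount over AUC0-∞, and the AUC0-∞ extrapolation rule stops short of the parameters built on AUC0-∞

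*SAP*

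**What the plan says.** **Urine parameters.** SAP 10.3.1 defines A_eu as the "amount excreted in urine over sampling interval (t1-t2) where t1 and t2 are the start and end times of the sampling interval" and gives Cumulative A_eu its own row as the sum over intervals. The CL_R row then reads "renal clearance, where $CL_R = A_{eu}/AUC_{0-\infty}$ (for BVD-523 only". The text after the tables keeps the two apart: A_eu is concentration times urine weight for one interval, and the cumulative amount over 0-x adds the "values for each collection interval over the 0-x hour period". Protocol 7.3 has "renal clearance, where $CL_R = A_e/AUC_{0-\infty}$ (for BVD-523 only". A_e without the u is defined neither there nor in the protocol's abbreviation list.

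**Sampling window.** Protocol 4.1 states: "Blood/plasma, urine, and fecal samples will be collected for bioanalytical, radioanalytical, and metabolism analysis through 168 hours postdose". For a later discharge, "additional samples (blood/plasma, urine, and fecal) for radioanalysis will be collected every 24 hours until Discharge". The Synopsis sets the same limit ("will be obtained through 168 hours postdose"). Table 6-1 collects urine over 0–6, 6–12 and 12–24 h, then in 24-hour intervals. Every interval end up to 168 h has a scheduled plasma sample.

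**Early exit.** Protocol 5.3: "Subjects will be informed that they are free to withdraw from the study at any time and for any reason".

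**Extrapolation.** SAP 10.3.1.2 flags AUC0-∞ at 20–30% extrapolation and keeps it in the descriptive statistics. Above 30% it is reported but excluded from them. Only AUC0-∞ is named. SAP 10.3.2.2 sets only no-result and not-calculated values to missing in parameter summaries.

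**The concern.** There are two faults of definition.

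1. The CL_R numerator is the symbol for one collection interval, while the denominator is the whole exposure. Followed as printed, the formula gives a different value for each interval, and none of them is renal clearance. The protocol's undefined A_e does not settle the matter, and the SAP states that it supersedes the protocol's statistical considerations. Even with the cumulative amount, nothing says what CL_R is for a subject whose urine collection ends early. A truncated amount over an AUC extrapolated to infinity is biased low.

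2. An AUC0-∞ above 30% extrapolation is judged unfit for the summary, yet it is still reported, so it is neither no-result nor not-calculated. CL_R and the AUC0-∞ ratios take AUC0-∞ by printed formula, so as written they stay in the descriptive statistics, on a different n from the AUC0-∞ they came from. The SAP prints no formula for CL/F and Vz/F. The same holds for them if, as is usual, they are computed from AUC0-∞.

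Pharmacokinetics and routes of elimination are the primary objective, and CL_R is one listed parameter under it. Recovery in urine and feces, which mainly carries the routes of elimination, is not affected, nor are the AUC0-12 and AUC0-24 ratios.

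**Working it through.** The documents give no CL_R value to reproduce, so the size is illustrated with a model.

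**Inputs** (Protocol 2.1.2): half-life 9 to 11 h in patients; Tmax 3.1 h (fasted median, food-effect study) to 4 h (upper patient median at 300–900 mg BID); fed Tmax 6.1 h as a sensitivity. Sampling times are from Table 6-1.

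**Assumptions:** one compartment, first-order absorption, constant renal clearance, AUC0-∞ scaled to 1, true half-life used for λz.

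**Formula.** Fraction of exposure, and so of urinary parent, after time t = (ka·e^(−kt) − k·e^(−ka·t))/(ka − k), with k = ln2/half-life and ka solved from Tmax.

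**Step 1: share of urinary parent per interval (%)**

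| Half-life, Tmax | 0–6 h | 6–12 h | 12–24 h | 24–48 h | 48–72 h |
|---|---|---|---|---|---|
| 9 h, 3.1 h | 30.8 | 25.6 | 26.3 | 14.6 | 2.3 |
| 11 h, 4 h | 24.3 | 23.7 | 27.6 | 19.1 | 4.2 |

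The largest share, including the 6.1 h sensitivity, is 31.3% (12–24 h; half-life 9 h, Tmax 6.1 h). The cumulative amount over 0–168 h is at least 99.99%.

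**Step 2: CL_R with the cumulative amount.** The SAP's linear trapezoidal rule is used throughout, with plasma stopping when urine stops.

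| | 9 h, 3.1 h | 11 h, 4 h |
|---|---|---|
| Completer AUC0-∞ | 1.0632 | 1.0559 |
| Completer CL_R, % of true | 1/1.0632 = 94.1 | 1/1.0559 = 94.7 |
| Cumulative urine 0–24 h | 0.8269 | 0.7557 |
| AUC0-24 + extrapolated tail | 0.8434 + 0.1731 = 1.0165 | 0.7668 + 0.2443 = 1.0111 |
| 24 h stop, over AUC0-∞ | 0.8269/1.0165 = 81.3% | 0.7557/1.0111 = 74.7% |
| 24 h stop, over AUC0-24 | 0.8269/0.8434 = 98.0% | 0.7557/0.7668 = 98.6% |

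Completers fall short of 100% because the linear trapezoid between 24 and 48 h overstates AUC. The 99.99% in step 1 is therefore a urinary amount and does not describe the accuracy of CL_R. A stop at 48 h gives 90.5–92% over AUC0-∞.

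**Step 3: effect of one 24 h stopper on the mean, relative to all completers** = (1 − stopper/completer)/n.
- 9 h, 3.1 h: 1 − 81.3/94.1 = 0.136, so 2.3% (n=6) or 3.4% (n=4).
- 11 h, 4 h: 1 − 74.7/94.7 = 0.211, so 3.5% (n=6) or 5.3% (n=4).

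The matched ratio moves the mean slightly the other way: (98.0/94.1 − 1)/6 = 0.7% upward at n=6.

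**Step 4: when the extrapolation rule would act.**
- BVD-523, last measurable sample at 48 h: 2.6–5.1% extrapolated. At 24 h: 0.1731/1.0165 = 17.0% to 0.2443/1.0111 = 24.2%.
- If plasma and urine both end at 12 h, extrapolation is 44–52%. AUC0-∞ would then be excluded, while a CL_R of 48–57% of true would stay in.
- For radioactivity and metabolites, treated with the same model, more than 30% needs a half-life above about 27, 41, 55 or 96 h when the last measurable sample is at 48, 72, 96 or 168 h. The 20% flag needs about 20, 31, 41 or 72 h. The documents give neither these half-lives nor the quantification limits.

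**The case against.** The best defence is that this is a slip of notation. Parameters are calculated per subject, a denominator running to infinity pairs only with a total amount, and a pharmacokineticist would use the cumulative sum. That stands. A reader might infer that reported CL_R would be about a third or less of its true value, but the documents do not support expecting that result; the 31% shows only that the printed formula cannot be right.

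A reader might also infer that the urine window is open to Day 15. It is not: samples after 168 h are for radioanalysis only, so for completers the BVD-523 window is fixed and only the symbol needs correcting.

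Nor is early stopping wholly unregulated. Parameters are calculated only where they can be, the PK Population requires evaluable data, deviations are weighed before lock, and a subject who vomits early may be excluded. Subjects are confined to at least Day 8 unless they leave early, and the documents give no likelihood of early exit. These provisions narrow the gap, but none says how CL_R is formed from a truncated collection.

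On extrapolation, %AUC_extrap is itself a listed parameter, so affected subjects could be identified; the SAP simply does not say what to do with their derived values. The accompanying table shells were not available and could carry a footnote on either matter.

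**Conclusion.** Both parts hold on the text. The printed CL_R formula is wrong, and the extrapolation rule, followed as written, leaves derived parameters in the summaries after their AUC0-∞ has been removed. Severity is minor: the study is descriptive, with six subjects enrolled so that at least four complete.

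With the intended cumulative numerator, completers sit at about 94–95% of true CL_R. One subject stopping at 24 h sits at 75–81% unmatched and about 98–99% matched, and would lower the mean by about 2.3–3.5% (n=6) or 3.4–5.3% (n=4). These sizes rest on the one-compartment model, a half-life taken from patients, Tmax of 3.1–4 h, and plasma stopping with urine.

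A reader might infer that the extrapolation gap will distort the BVD-523 summaries. With sampling to 168 h and a half-life of 9 to 11 h that is unlikely. For total radioactivity and metabolites, whether it acts is unknown. Confidence is high on the text and moderate on the consequences.

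**What to change.** 1. In SAP 10.3.1, write CL_R for BVD-523 as Cumulative A_eu over 0–168 h divided by AUC0-∞, and state that the protocol's A_e has this meaning.
2. Where urine collection ends early, let x be the end of the last complete urine interval and use Cumulative A_eu 0-x divided by AUC0-x over the same window. If plasma at x is below quantification and set to missing under SAP 10.3.1.1, use AUC0-∞ instead, provided it meets the extrapolation rule.
3. In SAP 10.3.1.2, apply the 20–30% flag and the exclusion above 30% also to CL_R where it uses AUC0-∞, to the AUC0-∞ ratios if either numerator or denominator fails, and to CL/F and Vz/F if they are computed from AUC0-∞.

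The cost is a few SAP sentences and one programming flag, with no change to sampling or conduct. The downside is a possibly smaller n for a few derived parameters.

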6.2.2 Subject Number and Identification

Subjects will be assigned a number by clinical site staff. Assignment of numbers will be in ascending order and no numbers will be omitted. Subject numbers will be used on all study documentation. For subjects who are withdrawn by the Investigator (or designee) or who voluntarily withdraw prematurely from the study, replacement subjects will be enrolled only if deemed necessary by the Sponsor. Replacement subjects will be assigned a subject number by adding 100 to the number of the subject they are replacing (eg, Subject No. 105 replaces Subject No. 005).

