6. STUDY DESIGN

This study will be an open-label, absorption, metabolism, and excretion study of [¹⁴C]-BVD-523 administered as a 600-mg (approximately 200 μCi) oral dose to 6 healthy male subjects following a 2-hour fast from food (not including water) that follows breakfast.

A schematic of the study design is presented in Figure 1. The start of the study is defined as the date the first subject signs an Informed Consent Form (ICF). This is specifically for a subject enrolled (assigned a dose) in the study and does not include screen failure subjects. A subject who completes all PK, radioactivity, and metabolism sampling prior to Discharge is considered to have completed the study. This is the last planned contact with the subject, and does not include any unplanned follow-up (eg, return to the clinic for repeat clinical laboratory test).

The end of the study is defined as the date the last subject completes the study. The planned duration of study conduct for each subject is up to 43 days (Screening through Discharge).

Figure 1 Study Design Schematic

Screening	Check-in	Dosing	PK/Radioactivity Sampling	Study Completion ^a
Days -28 to -2	Day -1	Day 1	Day 1 to Study Completion	Day 8 to Day 15
				

CRU = Clinical Research Unit; PK = pharmacokinetic.

^a Subjects will be discharged from the CRU starting on Day 8 if plasma radioactivity levels are below the limit of quantification, ≥90% of the radioactive dose is recovered, and if ≤1% of the radioactive dose is recovered in urine and feces for 2 consecutive 24-hour collection intervals. If these criteria are not satisfied by the morning of Day 8, subjects will continue to be confined in the CRU until these criteria are met, up to a maximum of Day 15.

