9. DEFINITION OF ANALYSIS POPULATIONS

The **All Subjects Population** will consist of all subjects who are enrolled in the study (signed the ICF) and have study assessments recorded in the electronic Case Report Form (eCRF).

The **Safety Population** will consist of all subjects who receive study drug and have at least 1 postdose safety assessment.

The **PK Population** will consist of all subjects who receive study drug and have evaluable PK data. Subjects may be excluded from the PK summary statistics and statistical analysis if a subject has an adverse event (AE) of vomiting that occurs within approximately 2 times median time to maximum concentration (T_{max}).

All protocol deviations that occur during the study will be considered prior to database lock for their severity/impact and will be taken into consideration when subjects are assigned to analysis populations. Details of subject assignment to the analysis populations will be listed.

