10.3.1.2 Criteria for the Calculation of an Apparent Terminal Phase Half-Life

- **Number of Data Points**

- At least 3 data points will be included in the regression analysis and preferably should not include C_{\max} .

- **Goodness of Fit**

- When assessing terminal phases, the R^2 adjusted value will be used as a measure of the goodness of fit of the data points to the determined line.
- An terminal phase half-life will only be calculated if the R^2 adjusted value of the regression line is greater than or equal to 0.7.

- **Period of Estimation**

- Time period used for the estimation of apparent terminal phase half-lives, where possible, will be over at least 2 half-lives.
- Where an elimination half-life is estimated over a time period of less than 2 half-lives, it will be flagged in the data listings at the discretion of the Pharmacokineticist, and the robustness of the value should be discussed in the study report.

- **Calculation of AUC**

- The minimum requirement for the calculation of AUC will be the inclusion of at least 3 consecutive plasma concentrations above the lower limit of quantification (LLOQ), with at least 1 of these concentrations following C_{\max} . Exceptions may be made for metabolites.
- For any partial AUC determination (ie, AUC_{0-12} and AUC_{0-24}), nominal time will generally be used for the end of the interval. Actual times for partial AUC intervals may be used at the discretion of the Pharmacokineticist.

- $AUC_{0-\infty}$ values where the percentage extrapolation is less than 20% will be reported. $AUC_{0-\infty}$ values where the percentage extrapolation is 20% to 30% will be flagged and included in the descriptive statistics, whilst $AUC_{0-\infty}$ values where the percentage extrapolation is greater than 30% will be reported but excluded from descriptive statistics.

- **Anomalous Values**

- If a value is considered to be anomalous due to being inconsistent with the expected PK profile, it may be appropriate to exclude this point from the PK analysis based on the Covance SOP. However, the exclusion of data must have strong justification and will be documented in the raw data and study report.
- Positive predose value(s) greater than 5% of C_{max} may be excluded from the summary statistics of PK tables and statistical analysis at the discretion of the Pharmacokineticist and BioMed Valley Discoveries Inc.

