10.3.2.2 Presentation of Pharmacokinetic Parameters

- For the calculation of summary statistics of PK parameters, all NR and NC values in a data series will be set to missing.
- The AUC values will be set to NC if they have been calculated using fewer than 3 concentrations, and/or 3 concentrations if the last is C_{\max} (exception made for metabolites).

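### Does the lack of a completeness rule for excreta let an early leaver's partial sum distort mean cumulative recovery?

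*SAP*

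**What the plan says.** The SAP, section 10.3.1, defines the fecal quantity as "cumulative percent of dose excreted in feces, calculated as the sum of the percent of dose excreted in feces for each collection interval", and the urinary one in the same way. Section 10.3.3 then applies mean, SD, median, minimum, maximum and n to the PK parameters.

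On who contributes:

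- Protocol synopsis: "Six healthy male subjects will be enrolled and dosed on Day 1 to complete at least 4 subjects". Protocol 6.2.2 makes replacement optional: "replacement subjects will be enrolled only if deemed necessary by the Sponsor".
- SAP 6, on completion: "A subject who completes all PK, radioactivity, and metabolism sampling prior to Discharge is considered to have completed the study".
- SAP 9: the PK Population "will consist of all subjects who receive study drug and have evaluable PK data". Evaluable is not defined further. The one subject-level exclusion is discretionary: "Subjects may be excluded from the PK summary statistics and statistical analysis if a subject has an adverse event (AE) of vomiting" within about twice the median Tmax.

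On incomplete data, the explicit rules are for AUC. SAP 10.3.1.2 says that AUC0-∞ "values where the percentage extrapolation is greater than 30% will be reported but excluded from descriptive statistics", and SAP 10.3.2.2 adds: "The AUC values will be set to NC if they have been calculated using fewer than 3 concentrations". Nothing comparable is written for cumulative excretion.

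Protocol 3.2.1 lists total recovery in both excreta as an endpoint. The SAP parameter tables give urine and feces separately and no combined figure.

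**The concern.** Routes of elimination are part of the primary objective, and cumulative recovery by route is a natural summary of them. A sum that skips uncollected intervals treats them numerically as zero. If such a sum is averaged with complete ones, the mean falls and the SD rises, and truncated collection can be mistaken for poor mass balance or high between-subject variability.

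The plan tolerates two non-completers out of six, so the case is foreseeable. The discharge rule uses each subject's recovery during the study, so a later decision on whether a non-completer counts would be made with his value known. The contrast with the explicit AUC rules makes the silence on excreta look like an oversight.

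**Working it through.** The documents state no figure to reproduce. There is no expected recovery, no route split and no dropout rate, and the sample size rests on precedent. The check is therefore textual first and illustrative second.

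**1. What the text does with a subject who leaves at 24 h**

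Under the footnotes to Protocol Table 6-1, the 0-168 h window holds:

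- urine: 3 intervals on the first day plus (168 − 24)/24 = 6 daily intervals, so 9;
- feces: 1 + 6 = 7 intervals.

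This subject has 3 of 9 urinary and 1 of 7 fecal intervals. Entering his sum as a 0-168 h value would set six intervals of each kind to zero. Against that:

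- SAP 10.3.1 calculates excretion parameters only where possible, and builds cumulative urinary amount for a 0-x hour label from the intervals in that window.
- SAP 10.1 rules out imputation of missing values.
- SAP 10.3.2.2 sets NC and no-result values to missing in parameter summaries.
- SAP 9 requires evaluable data and considers protocol deviations before lock when assigning subjects to populations.

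Read together, his 0-24 h value is usable and his 0-168 h value is most naturally missing. This is the natural reading, not a forced one. The 0-x wording covers urinary amount only, and summing what was collected is not strictly imputation.

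**2. The comparison with AUC**

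The 30% rule limits the extrapolated part of AUC0-∞. A cumulative excretion figure has no extrapolated part. The closer analogue is AUC0-t cut short by withdrawal, which has no completeness rule beyond a minimum number of concentrations. The SAP is not clearly looser on excreta than on its other observed, truncated quantities.

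**3. Size under the less natural reading**

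Assumptions: each completer recovers 30% in urine and 60% in feces, total 90% (borrowed from the discharge threshold), and j of 6 leave with r% recovered.

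Mean = [(6 − j)·90 + j·r]/6 = 90 − (j/6)(90 − r)

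| r (%) | j = 1 | j = 2 |
|---|---|---|
| 25 | 79.2 | 68.3 |
| 60 | 85.0 | 80.0 |
| 80 | 88.3 | 86.7 |

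By route, with r = 25 taken as urine 20 and feces 5:

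- urine: (5·30 + 20)/6 = 28.3 for j = 1; (4·30 + 2·20)/6 = 26.7 for j = 2;
- feces: (5·60 + 5)/6 = 50.8 for j = 1; (4·60 + 2·5)/6 = 41.7 for j = 2.

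With spread among completers (94, 93, 93, 87, 86, 85), the mean is 89.7 and the SD 4.1. Replacing 85 by 25 gives mean 79.7 and SD 27.0. The five completers alone give 90.6 and 3.8.

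The median behaves differently. With equal completers and j of at most 2, the third and fourth ordered values are both completers' values, so it stays at 90. In the spread example it is (87 + 93)/2 = 90 before and after. In general, two low leavers among six leave the median within the completers' range.

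**4. How a subject would leave early**

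The tolerated number is 6 − 4 = 2. The early exit that Protocol 4.1 describes is emesis in the first 4 h, with possible same-day discharge. Protocol 6.2.3 notes that such subjects could be replaced. The SAP 9 window is about twice the median Tmax. Taking the food-effect study's medians as a guide, that is 2 × 3.1 = 6.2 h or 2 × 6.1 = 12.2 h, and both cover 4 h. What remains is other withdrawal from a confined single-dose study. In the 14 healthy volunteers dosed at 600 mg (Protocol 2.1.2), no TEAE led to discontinuation.

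**5. The combined total**

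Per subject it is cumulative urinary plus cumulative fecal percent, both listed. With the same n, the mean total is the sum of the route means: 30 + 60 = 90, or 28.33 + 50.83 = 79.17 in the one-leaver case. The SD, median and range of the total do not follow in that way. SAP 4 bases analyses on the protocol unless modified and places output detail in the TFL shells. SAP 10.3.1 has total-radioactivity excretion reported by the radioanalysis group and allows additional parameters.

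**The case for a change.** The strongest case for change is that a written criterion is cheap and the existing safeguards do not force the right answer. Plasma rules need not catch an early leaver. Assume one-compartment kinetics, a 9 to 11 h half-life (Protocol 2.1.2) and Tmax near 3 h. A last sample at 24 h then leaves 2^(−24/t½)·ka/(ka − k) extrapolated, which is 0.157 × 1.09 = 17% to 0.220 × 1.07 = 24%. That AUC is at most flagged and still summarised, so the subject stays evaluable for plasma while his excreta collection is short. The vomiting exclusion is optional and covers no other withdrawal. Protocol 7.4 also allows missing-data procedures to be set out in the study report, after the values are known.

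This much stands: the SAP states no excreta criterion, and the total is not named there. The harm is limited. No hypothesis is tested. SAP 10.1 lists data up to withdrawal with excluded subjects highlighted, SAP 10.2 summarises disposition, and the summaries carry n, median and minimum. A truncated sum among six listed men would be visible.

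The obvious remedy, summarising only those who completed the study, also misfires. SAP 6 ties completion to all PK, radioactivity and metabolism sampling. Read literally, one missed blood draw would remove a subject whose excreta are complete. Flagging a completer's lost fecal collection without excluding it would leave a partial sum in the mean.

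**Conclusion.** No change to the plan is called for. The SAP leaves a rule unwritten, but it does not prescribe a wrong one. Its provisions on calculability, imputation, 0-x windows and evaluability lead an analyst to treat a non-collector's 0-168 h recovery as missing, and the total is simple addition that the TFL shells or radioanalysis report, which were not available, may already contain.

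The shift in the mean, down to 79.2% with one leaver or 68.3% with two at r = 25, depends on three things together: withdrawal not covered by the emesis provisions, the less natural reading of the sum, and assumed recoveries of 90% and 25%. It shrinks to 1.7 points (90 − 88.3) for one leaver who has already recovered 80%, and is zero if all six complete. A sentence on excreta completeness would be a harmless clarification, but its absence is not a demonstrated error.
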